7. RISKS

a. Potential Risks

i. Investigational devices

Mania/hypomania and/or seizure.

Currently, no known cases of either risk in iTBS according to a review in The Journal of Nervous and Mental Disease (Rachid 2017).

According to a review published in the International Journal of Neuropsychopharmacology, there have been 4 cases of treatment-emergent mania induced using rTMS (3 bipolar patients, 1 MDD patient) (Xia et al. 2008).

FDA approved rTMS has a 1:30,000 chance of seizure.

Additionally, the following expected AEs were reported in association with TMS in a recent publication (Downar et al, 2018): Headache, nausea, dizziness, fatigue, insomnia, anxiety or agitation, back or neck pain, vomiting, tinnitus, migraine aura, abnormal sensations, unrelated accidents, and unrelated medical problems such as cold and flu.

Citation:

Downar et al (2018). Effectiveness of theta burst versus high-frequency repetitive transcranial magnetic stimulation in patients with depression (THREE-D): a randomized non-inferiority trial. *The Lancet*.

ii. Investigational drugsNA

iii. Commercially available drugs, biologics, reagents or chemicalsNA

iv. Procedures

Mania/hypomania and/or seizure.

v. Radioisotopes/radiation-producing machinesNA

vi. Physical well-being

Participants will have all measures exerted to reduce the chances of seizure and discomfort from stimulation.

vii. Psychological well-being

Participants will be placed in a relaxing environment. We do not anticipate that there would be any worsening.

viii. Economic well-being

Participant's economic well-being may benefit from the intervention, as they may receive an intervention that would normally cost thousands of dollars in the clinic and is not covered by most insurers.

ix. Social well-being

We would anticipate that particularly the responders that perceived social wellbeing would improve. We do not anticipate that there would be any worsening.

x. Overall evaluation of risk

Low - innocuous procedures such as phlebotomy, urine or stool collection, no therapeutic agent, or safe therapeutic agent such as the use of an FDA approved drug or device.

b. International Research Risk Procedures

NA

c. Procedures to Minimize Risk

We will have a trained rTMS treater in the room at all times monitoring for changes in level of consciousness. We will eliminate any offending agents that may increase risk of seizure.

Monitoring participants depressive symptoms will allow the identification of individuals at risk of suicide and therefore the risk of this occurring can be minimized. The patient's psychiatrist will be immediately notified if participants show signs of suicidal ideation or display depressive symptoms which are worse than baseline (by 5 points on the HAMD compared to the HAMD score the patient had before study enrollment. If any study personnel believe a participant is at risk, the PI [name] (a psychiatrist) will be notified immediately and an emergency consultation between him and the participant will be had. If the PI considers it necessary, the patient will be referred for emergency psychiatric treatment.

If any participant displays an increased YMRS score ($>/=2$ points) on 2 questions, stimulation will be stopped to prevent any possibility of inducing hypomania or mania. If any of the research team or clinical staff believe that the participant may be showing signs of hypomania/mania, the YMRS will be administered by trained personnel immediately, the researchers will not wait until the daily assessments are conducted.

d. Study Conclusion

The experiment will terminate when the final participant has completed their treatment and all data has been analyzed.

e. Data Safety Monitoring Plan (DSMC)

i. Data and/or events subject to review

Adverse events, protocol deviations, aggregate data will all be frequently reviewed by the monitoring board (PD).

ii. Person(s) responsible for Data and Safety Monitoring

The Protocol Director.

iii. Frequency of DSMB meetings

NA

iv. Specific triggers or stopping rules

If there is evidence of significant risk to the participants such as multiple seizure events or worsening of psychiatric state in a large majority of the participants.

v. DSMB Reporting

NA

vi. Will the Protocol Director be the only monitoring entity? (Y/N)

Yes.

vii. Will a board, committee, or safety monitor be responsible for study monitoring? (Y/N)

NA

f. Risks to Special Populations

NA.

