The subjects will undergo an MRI scan of the brain that will require about 1 hour in the MRI scanner. A structural MRI scan and an fMRI scan will be done using a 3T system at Stanford facilities.

During the scan, subjects will lie on the table in the magnet for 1 hour while the images are acquired. Instructions may be given through an auditory system. Subjects will wear earplugs and may be fitted for a bite bar to help them to keep their head still during the scans; for studies that enroll older adults, a bite bar will not be used so as to accommodate participants with dentures. These procedures have been used previously in younger and older adults alike, and do not cause undue distress in subjects. Brain images will be made using conventional MRI imaging (including functional and diffusion tensor

imaging).

Patients will undergo a minimum of 3 scans up to a maximum of 6 scans, each 1 hour in length.

Acquisition and data extraction:

Clinical interview ratings will be made by trained study personnel. Individual item scores will be recorded and then summed according to symptom cluster and scale definitions.

Outcome measures:

The primary outcome measure for this study will be change in MADRS score. The MADRS is a clinical assessment tool used to rate a patient's level of depression and is the standard scale used for depression research studies.

Secondary measures will include functional connectivity change of the sgACC to the DMN. Primary outcome will be assessed as the change between baseline and immediate post-stimulation, with secondary measures to include the change between baseline and immediate post- stimulation and 1-month post-stimulation.

Other secondary measures include clinical interview assessments, to be performed according to the timeline above, include:

HAMD-17 (Hamilton Depression Rating Scale 17-Item)
C-SSRS (Columbia Suicide Severity Rating Scale)
HAMD-6 (Hamilton Depression Rating Scale 6-Item)
MADRS (Montgomery-Asberg Depression Rating Scale)

b. Procedure Risks

These methods are the least risky because the intervals of stimulation have been shown to be appropriate for theta burst stimulation in the motor system with no adverse outcomes.

We don't anticipate any risk from the procedures themselves, aside from those mentioned in section 7a i.

c. Use of Deception in the Study

NA

d. Use of Audio and Video Recordings

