We will be video and audio record study participants during the consent process and clinical assessments conducted with them while enrolled in the study. The video and audio recordings will be recorded using Zoom video from an encrypted Stanford owned laptop. The recordings will be available for training purposes for study personnel only or as otherwise consented to on the consent form. We will not use or distribute the recordings to outside personnel or scientific meetings etc. unless directly indicated by the participant on the video consent form attached in section 13

e. Alternative Procedures or Courses of Treatment

Participants with insurance could alternatively receive traditional rTMS.

f. Will it be possible to continue the more (most) appropriate therapy for the participant(s) after the conclusion of the study?

The participants will have the option of pursuing treatment as usual after the study (medications, therapy, traditional rTMS).

g. Study Endpoint(s)

The study will end 6 months after the last participant completes their visit.

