- Participants may currently be on a stable and adequate dose of SSRI antidepressant therapy. Participants may choose to not be on antidepressant therapy for the study duration, or to be switched from other classes to a medication from the SSRI class.
- Participants may also have a history of intolerance to at least 2 antidepressant medications. These patients with the intolerance history will not be required to be currently taking an antidepressant medication.
- Participants must qualify as "Moderately Treatment Refractory" or "High Treatment Refractory" using the Maudsley staging method.
- Meet the threshold on the total HAMD17 score of ≥ 20 at both screening and baseline visits (Day -5/-14 and Day 0).
- Meet the threshold on the total MADRS score of ≥ 20 at both screening and baseline visits (Day -5/-14 and Day 0).
- Meet the threshold on the total BDI-II score of ≥ 20 at both screening and baseline visits (Day -5/-14 and Day 0).
- In good general health, as ascertained by medical history.
- If female, a status of non-childbearing potential or use of an acceptable form of birth control. The form of birth control will be documented at screening and baseline.
- Concurrent hypnotic therapy (e.g., with zolpidem, zaleplon, melatonin, or trazodone) will be allowed if the therapy has been stable for at least 4 weeks prior to screening and if it is expected to remain stable.

ii. Exclusion Criteria

- Female of childbearing potential who is not willing to use one of the specified forms of birth control during the study.
- Female that is pregnant or breastfeeding.
- Female with a positive pregnancy test at participation.
- Total HAMD17 score of < 20 at the screen or baseline visits.
- Total MADRS score of < 20 at the screen or baseline visits.
- Total BDI-II score of < 20 at the screen or baseline visits.

- Current diagnosis of a Substance Use Disorder (Abuse or Dependence, as defined by DSM-IV-TR), with the exception of nicotine dependence, at screening or within six months prior to screening.
- Current diagnosis of Axis I disorders other than Dysthymic Disorder, Generalized Anxiety Disorder, Social Anxiety Disorder, Panic Disorder, Agoraphobia, or Specific Phobia (unless one of these is comorbid and clinically unstable, and/or the focus of the participant's treatment for the past six months or more).
- History of schizophrenia or schizoaffective disorders, or any history of psychotic symptoms in the current or previous depressive episodes.

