The Primary Mechanistic Outcome Measure for this study is percent change in MADRS scoreat one-month post treatment. **The Relevant Clinical Outcome Measure** is a reduction in depressive symptoms in treatment resistant outpatients diagnosed with MDD, as measured

by change in MADRS score. For secondary aims, the emphasis is on identifying the magnitude of effects (clinical significance, effect size) instead of statistical significance. Following the convention in imaging studies, we will conduct our primary analyses treating the contrast (baseline versus post) as one univariate outcome. We do not expect much variation across our narrowly defined subjects, although some variation is still possible. Given that, we will also analyze the data in the linear mixed effects modeling framework allowing for random intercepts (although this is not customary in imaging studies) as a way of sensitivity analysis.

Moderator/mediator investigation: We will explore various baseline variables as potential moderators of aiTBS. For this investigation, we will employ the MacArthur approach for moderator analysis. We will also examine potential mediators of rTMS effect using the MacArthur approach as well as contemporary causal mediation approaches, which we believe will provide valuable insights regarding the neuromodulation mechanism for the next phase of investigation.

Handling of missing data: As a way of assessing the impact of missing scan sessions, we will repeat our main analyses treating outcomes measured in the pre-aiTBS scan and in the 1-month post-aiTBS scan as multivariate outcomes. This will allow us to include all participants in the analysis as long as two of the three scans are available. In this analysis framework, missing data will be handled assuming that it is missing at random conditional on observed scan session data (maximum likelihood estimation). Analyzing the data using both univariate and multivariate analysis approaches will also serve as sensitivity analyses. Additionally, we will include the order of scan sessions in the model to account for the carryover and order effects.

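### MADRS scores taken at one month after other treatment has begun would count as aiTBS benefit, and the plan neither records such treatment nor says how those scores are handled

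*Protocol*

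**What the plan says.** **Endpoint.** SAP section 9 (Data Analyses) makes the primary measure "percent change in MADRS scoreat one-month post treatment", and its Sample Size paragraph powers the study on MADRS change from baseline to one month. Protocol section 2a (Outcome measures) differs: "Primary outcome will be assessed as the change between baseline and immediate post-stimulation", with one month as a secondary time point. The one-month scan falls 25-30 days after the final stimulation (section 2a, Imaging and Biomarkers), and the baseline clinical assessments are repeated at that time point (Follow-up Time-Period).

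**Design.** All participants receive active stimulation. The primary analysis is a baseline-versus-post contrast with no control arm.

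**Route to other care.** Protocol section 7c states: "The patient's psychiatrist will be immediately notified if participants show signs of suicidal ideation or display depressive symptoms which are worse than baseline", the worsening being 5 HAMD points against the pre-enrollment score. Anyone thought to be at risk has an emergency consultation with the PI, and then: "If the PI considers it necessary, the patient will be referred for emergency psychiatric treatment".

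**Other treatment.** In section 6h(i), hypnotics are allowed if "stable for at least 4 weeks prior to screening and if it is expected to remain stable". SSRI use at entry must be stable and adequate. The same section also lets a participant go without antidepressants throughout, or change from another drug class to an SSRI. Section 2f says: "The participants will have the option of pursuing treatment as usual after the study (medications, therapy, traditional rTMS").

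**Handling.** The SAP's missing-data paragraph deals with missing scan sessions under a missing-at-random assumption. Neither document says what happens to a MADRS score taken after other treatment has begun.

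**The concern.** About four weeks separate the last stimulation from the score the SAP treats as primary. Any effective treatment that begins in that interval contributes to the score. Under section 7c the participants most likely to receive it are those doing worst, so it would raise the lowest changes. That lifts the mean change and also reduces its SD, and both increase a within-subject effect size and the paired t statistic. No control arm is exposed to the same process, so nothing offsets it.

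A participant who is referred and then misses the one-month visit does not remove the problem. A complete-case contrast loses a poor outcome, which biases in the same direction.

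What is at stake is any statement that the aiTBS effect lasts to one month. If treatment changes are not logged when they occur, routine outpatient changes may be impossible to separate out afterwards.

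**Working it through.** **1. The plan's own figure.** Inputs from SAP section 9, Sample Size: d = 0.6, two-sided alpha 0.05, power 80%, within-subject t-test.
- Normal approximation: ((1.960 + 0.842)/0.6)² = 21.8, so 22.
- Exact noncentral t: power 0.785 at n = 23 and 0.804 at n = 24, so 24.
- Recruitment: 23/0.8 = 28.75, so 29; 24/0.8 = 30.

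The stated 23 evaluable and 30 recruited are consistent with this and are not in dispute.

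**2. Effect on observed d.** The documents give neither the share treated nor the benefit, so these are assumptions:
- change in MADRS points (the scale of the power statement) is normal with mean 6 and SD 10, so d = 0.6;
- a share p receives other treatment worth x points;
- treatment goes to those lowest on a trigger that correlates ρ with the final change. ρ = 1 means exactly the worst final scores; ρ = 0.5 means imperfect targeting.

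Then
- mean = 6 + p·x
- variance = 100 + x²·p(1−p) − 2·x·10·ρ·φ(z_p)

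where φ(z_p) is the normal density at the p-quantile: 0.1755 for p = 0.10 and 0.2800 for p = 0.20.

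Worked case, p = 0.10, x = 5, ρ = 1: mean = 6.5; variance = 100 + 25(0.09) − 100(0.1755) = 84.7; SD = 9.20; d = 6.5/9.20 = 0.71.

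| Share | Benefit | d, ρ = 1 | d, ρ = 0.5 |
|---|---|---|---|
| 10% | 5 | 0.71 | 0.67 |
| 10% | 8 | 0.77 | 0.71 |
| 20% | 5 | 0.80 | 0.74 |
| 20% | 8 | 0.94 | 0.81 |

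With a 2-point benefit and 10% treated, d is 0.64 at ρ = 1.

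**3. Effect on the test when aiTBS does nothing.** Same set-up with mean 0 and n = 23, simulated. The chance of a significant improvement, nominally 2.5%, is 3.6-5.5% with 10% treated and 6.4-12.0% with 20% treated (x = 5 to 8, both values of ρ).

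**4. How large a share is plausible?** At mean 6 and SD 10, the proportion worsening by 5 points or more is Φ((−5 − 6)/10) = Φ(−1.1) = 14%. With no effect it is Φ(−0.5) = 31%. This treats HAMD and MADRS points as equal. Meeting the trigger is also not the same as being treated. With 23 analysed, two participants are 2/23 = 9%.

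**5. Check of the sensitivity rule.** With the worst 20% treated at true d = 0.6, scoring them simply as unchanged from baseline gives mean 7.60, SD 7.81 and d = 0.97. That is inflation in itself, because all of them lie below 6 − 8.4 = −2.4 points, already worse than baseline. Scoring them at the worse of baseline and their pre-treatment score returns d = 0.60, provided that score captures the untreated outcome.

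**The case against.** A reader might infer that the Protocol lets anyone who responds poorly start another antidepressant before one month, and that the one-month effect is therefore substantially inflated. The documents do not support that.

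- **Narrow route.** The explicit triggers are safety ones, and the explicit consequences are notification, PI consultation and discretionary emergency referral. Notification is not treatment. A non-responder who stays at baseline severity, without ideation or perceived risk, triggers nothing. That other antidepressant treatment could begin is inferred only from the absence of a bar.
- **Treatment as usual.** Section 2f places it after the study, and the one-month visit is part of the study. The entry wording on stable SSRIs, and on remaining off antidepressants throughout, also expresses an expectation of stability. Neither is a prohibition on change before one month.
- **Detection.** No clinical assessment is scheduled between the immediate-post and one-month visits. Worsening seen at the former could set section 7c in motion; later worsening has no scheduled detection point.
- **Records.** Emergency care would probably surface through adverse-event review (Protocol 7e; SAP Interim Analyses), so the recording gap matters mainly for routine outpatient changes.
- **Size.** Figures at the upper end need 20% treated and nearly perfect targeting. A 5-8 point gain within a month is itself an assumption in a population required to be moderately or highly treatment refractory.
- **Estimand.** Using scores as observed, whatever treatment followed, is a legitimate choice. It has to be stated, and without a control arm the result cannot then be attributed to aiTBS alone.

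These points limit the likely share and size. They do not supply a rule for affected scores or a record of routine changes.

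**Conclusion.** The gap is real. The SAP's primary score is taken about four weeks after stimulation in a single arm, an outcome-triggered route to other care exists, and no text bars or records treatment changes before that visit or says how later scores are treated. By default they count as aiTBS results.

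The direction is upward if the other treatment helps. The size cannot be derived from the documents. Under the stated assumptions it runs from modest (d about 0.67-0.77 instead of 0.6 with 10% affected) to material (0.74-0.94 with 20%). The false-positive tail is about 4-6% and 6-12% against 2.5%.

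The point bears on the one-month endpoint, which is the SAP's primary and a Protocol secondary. For the Protocol's primary, with scans 1-3 days after stimulation, it is close to nil. How much it matters therefore depends on which time point prevails, and the two documents must be reconciled on that.

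**What to change.** 1. At the immediate-post and one-month visits, log any antidepressant, augmentation agent, psychotherapy or neuromodulation started or changed since Day 5, with dates.
2. In the SAP, keep the as-observed analysis and pre-specify one sensitivity analysis in which an affected participant is scored at the worse of baseline and the last MADRS before the change. On the listed schedule, that last score will usually be the immediate-post one. The worse-of clause must stay, since scoring as unchanged can itself inflate the effect. Label the analysis a conservative bound, because it penalises partial responders.
3. Report the number affected, and base any claim of durability to one month on both analyses.
4. Reconcile the primary time point between Protocol section 2a and SAP section 9.

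The cost is a short log at two existing visits, one extra analysis of about 30 participants, and possibly a smaller reported one-month effect. No clinical rule and no access to care changes.

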4. DEVICES USED IN THE STUDY

a. Investigational Devices (Including Commercial Devices Used Off-Label)

Investigational Device 1	
Name:	MagPro X100 by MagVenture
Description:	Transcranial Magnetic Stimulation Device with theta burst stimulation.
Significant Risk? (Y/N)	No
Rationale for Non-Significant Risk	
The 'traditional 10Hz TMS' is on label and the theta burst stimulation is off label. It is the same device for both. The Magventure is about to be approved by the FDA for depression in 2 weeks. When that happens, the 'traditional 10Hz' stimulation will be on label with an approved device. The theta burst stimulation is minimal risk because the risk of seizure is very low (only reported once in literature) and there is no other risk other than minimal scalp irritation. We will be using an approved device 'off label' stimulation parameters which has a lower risk profile than the on label approved parameters.	
Investigational Device 2	
Name:	3T UHP MRI
Description:	MRI
Significant Risk? (Y/N)	No
Rationale for Non-Significant Risk	
The 3T Ultra-High Performance (UHP) MRI scanner from GE is an upgrade to the 3T MR750 which was a	

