Rationale for Study Design: The design will allow to assess the feasibility of modulating the neural circuitry underlying depression with accelerated intermittent theta-burst stimulation (aiTBS) alongwith the measuring the effects of this neuromodulation strategy on the underlying neural circuitry. The same subjects are utilized for all three MRI scan sessions, that is, for the pre-aiTBS scan session, the immediate post-aiTBS scan session and for the 1-month post-aiTBS follow-up scansession (to address functional connectivity aims). The rationale for using the same subject threetimes is to enable analysis of functional connectivity differences in the left DLPFC and dACC in response to aiTBS across time.

Sample Size

The study will be powered for an estimated effect size of Cohen's $d=0.6$ for change in Montgomery-Åsberg Depression Rating Scale (MADRS) between baseline and one month post treatment using within subject t-test. Prior investigations of iTBS of the L-DLPFC for treatment resistant depression reported an effect size of $d=1.337$, leaving our estimate conservative. We will set the probability of rejecting a true null hypothesis (Type 1 error, alpha) at 0.05 (two-sided) with 80% power. That will require a final sample size of 23 participants. This study will aim to recruit 30 individuals assuming approximately 20% missing data due to unusable imaging data or dropouts.

Interim Analyses and Stopping Rules

Because of the anticipated low level of adverse events of aiTBS and MRI, interim analysis of data,protocol and adverse events will occur by study staff at least once a year. Serious adverse events will be reviewed on a monthly basis, unless a more urgent review is requested. Only under extreme circumstances or if it were determined that a high level of side effects was due to aiTBS and/or MRI, would the PI be charged with breaking the study mask. This study will be stopped prior to its completion if: [1] the intervention is associated with adverse effects that call into question the safety of the intervention; [2] difficulty in study recruitment or retention will significantly impact the ability to evaluate the study endpoints; [3] any new information becomes available during the trial that necessitates stopping the study; or [4] other situations occur that might warrant stopping the study.

Data Analyses

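### A stop or urgent review after a first seizure is allowed but not required, and the routine review of serious adverse events is monthly while a full course takes 5 days

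*Protocol*

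**What the plan says.** **Stopping, protocol.** Item 7e(iv) sets a general test of significant risk to participants and illustrates it with events "such as multiple seizure events or worsening of psychiatric state in a large majority of the participants". It gives no count or denominator and does not say whether the response is a pause, a stop or a review.

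**Stopping, SAP.** Section 9, 'Interim Analyses and Stopping Rules', says the study will be stopped on any of four grounds. Two bear on this point: [1] "the intervention is associated with adverse effects that call into question the safety of the intervention" and [4] "other situations occur that might warrant stopping the study". Neither has a threshold, and the paragraph does not mention seizure.

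**Review timing.** The SAP states: "Serious adverse events will be reviewed on a monthly basis, unless a more urgent review is requested". General interim review by study staff is at least yearly. Protocol 7e(i) says only that adverse events are reviewed frequently, and 7e(vi) confirms that the Protocol Director is the only monitoring entity.

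**Safeguards.** Protocol 7c states: "We will have a trained rTMS treater in the room at all times monitoring for changes in level of consciousness". It also has stimulation stopped on a defined YMRS rise, and the PI told at once if staff think a participant is at risk.

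**Exposure and background risk.** All 30 participants receive 10 sessions a day for 5 days (protocol 2a). Protocol 7a(i) states: "FDA approved rTMS has a 1:30,000 chance of seizure". It knows of no case with iTBS, while 4a mentions one report with theta burst.

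**The concern.** Protocol 7a names two device risks, seizure and mania/hypomania. For mania, 7c gives a score-based stop. For seizure it gives detection, through the treater in the room, but no rule on what follows, either for the affected participant or for the others. The protocol's only seizure example is plural, and its example of psychiatric worsening needs most of the participants. Both point to a high bar. The SAP's grounds are broader but name no event that obliges anyone to act, and no event makes the more urgent review mandatory.

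The routine interval is also long against the treatment. A participant who starts the day after another's seizure would finish all 50 sessions within the week, well before a monthly review. At stake is whether later participants are exposed before anyone has to consider the first event. The MADRS, HAMD and connectivity analyses are not affected.

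**Working it through.** The plan attaches no probability to its stopping rule, so there is no figure of its own to reproduce. The check has two parts.

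**1. Timing.** One course is 5 × 10 = 50 sessions. The documents do not give the recruitment pace or the number of stimulators. Assuming one stimulator, no overlap and one course per working week, up to 4 courses (4 × 50 = 200 sessions) fit between monthly reviews.

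**2. Chance of a first and a second affected participant.** Inputs: n = 30 participants and 30 × 50 = 1,500 sessions (protocol 2a), and the rate 1/30,000 (protocol 7a(i)). The protocol does not say whether this rate is per participant or per session, so both readings are shown. It also describes approved rTMS, not this off-label schedule. The 1% and 5% rows are therefore assumptions that show a range; nothing in the documents supports either value.

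With independent participants and per-participant risk p:

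- P(at least one) = 1 − (1 − p)^30
- P(two or more) = 1 − (1 − p)^30 − 30p(1 − p)^29
- P(at least one in the next 4 courses) = 1 − (1 − p)^4

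On the per-session reading, p = 1 − (1 − 1/30,000)^50 = 0.17%.

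| Per-participant risk | At least one in 30 | Two or more in 30 | At least one in next 4 courses |
|---|---|---|---|
| 1/30,000 per participant | 0.10% | 0.00005% | 0.013% |
| 1/30,000 per session (0.17%) | 4.9% | 0.12% | 0.7% |
| 1% (assumed) | 26% | 4% | 4% |
| 5% (assumed) | 79% | 45% | 19% |

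Worked row, p = 0.05: 0.95^30 = 0.2146, so P(at least one) = 0.785. The one-event term is 30 × 0.05 × 0.95^29 = 0.339, so P(two or more) = 1 − 0.2146 − 0.339 = 0.446.

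At the quoted rate even one seizure in 30 would be unusual, and so informative about this schedule. If the plural example were used as a threshold, a true risk of 5% would fail to reach it in about 55% of trials of this size (100% − 45%).

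**The case against.** **The texts permit action after one seizure.** The protocol's wording is illustrative, SAP grounds [1] and [4] are broad, ground [1] says the study will be stopped if safety comes into question, and an urgent review can be requested at any time. This stands. A reader might infer that the plan rules out stopping until a second seizure, or that monthly is the fastest review available; the documents support neither. What remains is that action is allowed and not required.

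**Seizure is unlikely and precautions are in place.** This also stands. Epilepsy is an exclusion, a urine drug screen and the TASS are part of screening, sessions are 50 minutes apart, and agents that raise seizure risk are to be removed. At the quoted rate the expected number of seizures is close to zero. The point concerns a missing rule for a named risk, not a probable event.

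**In-room monitoring and PI notification already cover the event.** In part. They make it likely that a seizure is seen and reported at once. Read in context they act on the affected participant, and nothing in them makes other participants' courses wait.

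**Large exposure figures mislead.** This is right. If a first seizure occurs at a low risk and nobody reacts, its position among the 30 is about uniform and some 29/2 = 14.5 participants follow on average. A reader might infer that a pause rule would spare them. It would not: that figure assumes complete inaction, and under the fix the same Protocol Director may resume after a review.

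**The supplied SAP text begins at its section 9.** The statement that no pause is required applies to the text available.

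**Conclusion.** The point holds as a low-cost improvement to participant safety. Neither text requires a pause or a prompt review after a first seizure, the protocol's examples suggest a high bar, and the stated routine interval is several times the length of a course. The documents do not show that a seizure is likely, that a stop after one is barred, or that any efficacy result is at risk.

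The size depends on an unknown. At the quoted rate a first seizure has a chance of 0.1% or 4.9% over the trial, according to how the rate is read. The 26% and 79% figures rest on assumed risks of 1% and 5%. The four-course figure rests on an assumed pace. The case for the change does not depend on the higher rates: the rule would seldom be triggered if the quoted rate applies, and would matter if it does not.

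**What to change.** 1. In protocol 7e(iv), keep the general test and change the plural seizure example to 'a seizure'. Add a separate sentence there and in the SAP stopping paragraph: 'After any seizure, or any mania/hypomania that is a serious adverse event, the affected participant's stimulation stops, and no further stimulation is given to other participants until the Protocol Director has documented a safety review and the reason for resuming.' SAP grounds [1] to [4] stay.
2. In the SAP, replace the routine monthly review with: 'Each serious adverse event that occurs during or after stimulation and is possibly related to it is reviewed before the next participant starts a course; all other serious adverse events are reviewed monthly.' Unrelated events then do not delay treatment.
3. Keep the example of psychiatric worsening, but replace its large-majority qualifier with 'in several participants'. Deleting the qualifier altogether would make one participant's worsening a study-level example, and 7c already handles individual worsening.

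**Cost.** Wording in one protocol item and one SAP paragraph, with no new staff, board, visits or assessments. The chance of a seizure pause at the on-label rate is 0.1% or 4.9% over the trial. The chance of a pause for serious mania cannot be computed, because 7a(i) gives 4 cases without a denominator. A participant in mid-course may have the 5-day sequence interrupted, and a next course may be briefly delayed. The Protocol Director still decides, so what is gained is a prompt review with a recorded reason.
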